### **Aim 3:** To evaluate improvements during hospitalization.

Exploratory Hypothesis 3: Participants who receive MI-SI plus TAU will report greater reductions in SI during hospitalization, than participants who receive TAU alone.

Exploratory Hypothesis 4: In participants who receive MI-SI plus TAU, in-session living talk will be positively associated with reductions in SI during hospitalization.

Exploratory Hypothesis 5: In participants who receive MI-SI plus TAU, in-session suicide talk will be negatively associated with reductions in SI during hospitalization.

Exploratory Analyses 3-5: Data will be analyzed using GLMM to account for repeated measures within subjects  with a focus on within subject decreases in SI (assessed with SSI scores). A minimum of two GLMMs will be used to examine the effect of MI-SI on the severity of SI at 2-3 and 3-5 days after the baseline assessment, the strength of in-session living and suicide talk and the severity of SI at 2-3 and 3-5 days after the baseline assessment. We will also examine the associations between in-session living and suicide talk on the severity of SI over 1, 3, and 6 months follow-up.

Power Analysis: Recruitment will provide data on 112 participants. Assuming a retention rate of 80%, data on 90 participants will be available at the 6 month follow-up. To estimate the statistical power afforded by 90 participants for the severity of SSI, power analyses were conducted using STATA 11 101 "sampsi2" package, which uses calculations based on Frison and Pocock model. 102 Specifying method of analysis (change), number of baseline assessments (1), number of post assessments (3), correlation between baseline and follow-up scores (r = .50), correlation between follow-up scores (r = .70), and standard deviation (sd = 8.4) for the outcome variable using Frison and Pocock's recommendations and our pilot data. we would have .94 power to identify a 5-point difference in mean SSI scores between treatment arms, .81 power to identify a 4-point difference, and .60 power to identify a 3-point difference. The study would therefore be adequately powered to find an effect size of .5 for the primary outcome. If there is concern that the experimental intervention caused harm and the trial is not stopped, we will conduct two-sided analyses instead of the one-sided analyses we proposed. Power analyses suggest we will have .88 power to identify a 5-point difference, .71 power for a 4-point difference, and .47 power for a 3-point difference with the proposed 90 participants (45 in each group), indicating that the trial will still be fairly well powered.

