### **Analytical Plan**

**Data Preparation.** All data will be screened for missing data, outliers, non-normality, non-linearity, and non-homoscedasticity. A combination of statistics and graphic representations will be used to complete these screens. Specifically, missing values analyses, descriptive analyses, frequencies, scatter plots and histograms will be used. The assumptions underlying the proposed statistical analyses will also be tested, which may lead to data transformations or the use of more appropriate statistics. Additionally, imbalances in important covariates between randomized groups will be tested at baseline, which may lead to the identification of covariates to be included in the analyses. Findings will be used to fine-tune the analytical plan if statistical assumptions are unmet or model fit is poor. All analyses will be based on an intent-to-treat approach, analyzed as randomized, include all available data, use multiple imputation for missing data if appropriate, and use one-tailed tests with p < .05 as the cutoff for statistical significance. The study is not powered to test exploratory hypotheses, and we therefore do not

expect to detect significant differences between groups. If the analyses are reported as part of the primary RCT, we will use a p-value of .01 to define statistical significance.

**Aim 2:** To evaluate whether MI-SI plus TAU results in significant reductions in suicidal ideation (SI) and increases in treatment engagement when compared to TAU alone.

Primary Hypothesis: Participants who receive MI-SI plus TAU will report greater reductions in SI over follow-up than participants who receive TAU alone.

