Primary Analysis 1: An over-dispersion Poisson generalized linear mixed model (GLMM) with maximum likelihood estimation will be used to examine the effect of MI-SI on the severity of SI at 1, 3, and 6 months follow-up. GLMM was chosen because random effects are added to the model to account for repeated measures within subjects. An over-dispersion Poisson GLMM will be used because the SSI is bounded at zero and had a standard deviation larger than the mean at follow-up in our pilot data, indicating over-dispersion. If data do not meet the assumptions of a Poisson distribution, we will use a negative binomial or zero-inflated negative binomial. The benefit of using maximum likelihood estimation is that it yields unbiased estimates in the presence of missing data, if data are missing at random. Because participants may receive one or two sessions of MI-SI, and the change pattern may not be linear over time, we will test sessions of MI-SI, time of assessment, and their interaction in follow-up analyses. As an added measure of clinical significance, we will report the number of participants in each group who fall below the two-point cut-off.

Because the presence of any suicidal behavior (i.e., attempted suicide, interrupted attempts, preparatory behavior) is an important outcome, we will use a mixed effects general logistic model to examine the effect size of MI-SI on the incidence of suicidal behavior as measured by the C-SSRS over follow-up assessments.

Exploratory Hypothesis 1: Participants who receive MI-SI plus TAU will engage in more treatment over follow-up than participants who receive TAU alone.

Exploratory Analysis 1: Multivariable logistic regression will be used to examine the effect of MI-SI on treatment engagement. The Hosmer-Lemeshow statistic will be used to evaluate model fit, and odds ratios with 95% confidence intervals will be derived using the method of maximum likelihood.  Because participants may receive one or two sessions of MI-SI, we will conduct a sensitivity analysis examining the number of MI-SI sessions as a predictor of treatment engagement. Because this is an underpowered exploratory analysis, we will also conduct secondary analyses using other definitions of treatment engagement such as number of sessions attended.

We will also examine the impact of the intervention on use of the Safety Plan coping strategies. To test treatment differences, we will use a multivariable logistic regression.

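### The stated powers are correct for a normal change-score test with SD 8.4, but they are not the power of the planned count mixed model, and no printed pilot SSI SD is 8.4

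*Combined protocol and SAP*

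**What the plan says.** The Power Analysis paragraph (end of the Analytical Plan, under Aim 3) describes a Frison-Pocock calculation: "Specifying method of analysis (change), number of baseline assessments (1), number of post assessments (3"), with "correlation between baseline and follow-up scores (r = .50"), a correlation of .70 between follow-ups and an SD of 8.4. It attributes these inputs to the Frison-Pocock recommendations and the pilot data. The result is that "we would have .94 power to identify a 5-point difference in mean SSI scores between treatment arms, .81 power to identify a 4-point difference", with .60 for 3 points. From this the paragraph concludes that power is adequate for an effect size of .5 on the primary outcome.

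Tests are one-sided by default: "use one-tailed tests with p < .05 as the cutoff for statistical significance". If harm is a concern and the trial continues, "we will conduct two-sided analyses instead of the one-sided analyses we proposed". The stated powers are then .88, .71 and .47, described as still fairly good.

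Primary Analysis 1 (Analytical Plan, Aim 2) specifies a different test: "An over-dispersion Poisson generalized linear mixed model (GLMM) with maximum likelihood estimation will be used to examine the effect of MI-SI" on SSI at 1, 3 and 6 months. The fallback is a negative binomial or zero-inflated negative binomial model. The reason given is that SSI is bounded at zero and that its pilot follow-up SD exceeded its mean. No baseline SSI term is named.

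**The concern.** The plan sets aside a normal model because of how SSI is distributed at follow-up, then takes its power from a normal model with one constant SD. In a count model with the usual log link, the treatment effect is a ratio of means. A 4-point difference then has no fixed size until the arm means and the dispersion are given, and the plan gives neither a TAU mean, a rate ratio nor a dispersion. The sponsor therefore has no stated power for the test that decides the trial.

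The SD is a separate matter. Pilot SSI SDs are printed in Work Accomplished: 4.88 and 10.44 in Table 1 (N = 9), 9.19 and 9.32 in Table 2 (N = 11). None is 8.4.

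At stake is how a null result is read. A reader would set it against a claim of .81 power for 4 points, and that claim is not tied to the analysis that produced the result.

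**Working it through.** **Inputs from the documents.** One-sided .05; "with the proposed 90 participants (45 in each group"), which follows from "Assuming a retention rate of 80%, data on 90 participants will be available at the 6 month follow-up" (112 × .80 = 89.6); correlations .50 and .70; SD 8.4; pilot follow-up SSI mean 5.55, SD 9.32 (Table 2).

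**Assumptions, not in the documents.** A log link; MI-SI mean equal to the pilot's 5.55; TAU mean 5.55 + 4 = 9.55; alpha of .05 for the two-sided alternative.

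**1. The plan's own figures.** The change-score variance factor is (1 + 2 × .70)/3 + 1 − 2 × .50 = .80. The standard error is 8.4 × √.80 × √(2/45) = 1.584. Power is Φ(d/1.584 − 1.645) one-sided, and with 1.96 in place of 1.645 two-sided.

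| Points | One-sided (stated) | Two-sided (stated) |
|---|---|---|
| 5 | .935 (.94) | .884 (.88) |
| 4 | .811 (.81) | .714 (.71) |
| 3 | .598 (.60) | .474 (.47) |

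All six reproduce.

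**2. Same formula, printed follow-up SD.** The standard error is 9.32 × √.80 × √(2/45) = 1.757. Power for 5/4/3 points is .885/.736/.525 one-sided and .812/.624/.400 two-sided. An effect size of .5 at SD 8.4 is 4.2 points; power for 4.2 points falls from .84 to .77.

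**3. Log-ratio approximation, no baseline term, 4 points.** The effect is ln(9.55/5.55) = .543. The variance is (.80/45) × [(SD_MI/5.55)² + (SD_TAU/9.55)²], with SD_MI = 9.32.

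| TAU spread | SE | Closed-form power | Simulated power |
|---|---|---|---|
| SD 9.32 | .259 | .67 | about .72 |
| SD 10.44 | .267 | .65 | about .70 |
| Variance proportional to mean (9.32²/5.55 = 15.65, so SD = √(15.65 × 9.55) = 12.2) | .282 | .61 | about .66 |

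The simulation used correlated negative binomial counts, 45 per arm and three visits, and tested the log ratio of arm means with a subject-level robust SE. The underlying latent correlation was .7, which gives observed correlations of roughly .61 to .66. Raising it until the observed values are slightly above .70 lowers the simulated powers to about .63 to .69. Null rejection is about .057, so the test is slightly liberal.

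**4. Baseline handling.** With baseline SSI as a covariate, the normal-theory factor becomes .80 − .50² = .55. Power for 4 points is then .92 at SD 8.4 and .86 at SD 9.32. Putting .55 into the log-ratio formula gives .81, .79 and .75 for the three rows above.

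**5. Sensitivity to the TAU mean.** The TAU comparison data in Work Accomplished show a 9-point fall, which suggests 23.45 − 9 = 14.45. With means 10.45 and 14.45 and SD 9.32 in both arms, the closed form gives .71 for 4 points. If variance rose in proportion to the mean it would give .45, but that implies a TAU SD of √(15.65 × 14.45) = 15.0, well above any printed value.

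**The case against.** Closed-form repeated-measures power is a common planning approximation, and the paragraph presents itself as an estimate. A roughly constant SD can be defended from the pilot: the same 11 participants had an SD of 9.19 at mean 23.45 and 9.32 at mean 5.55. The value 8.4 lies within the printed range, the plan credits it partly to published recommendations, and an unprinted pilot SD (for all 13 participants, say) cannot be excluded. An SD from 11 people in a single-arm pilot at 60 days is itself imprecise. All of this stands. It makes the source of 8.4 unstated rather than the value wrong.

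The effect-size wording also survives step 2 when read in SD units. Power for half an SD is Φ(.5/√(.80 × 2/45) − 1.645) = .84 whatever the SD; at SD 9.32, half an SD is 4.66 points. It does not carry over to the count model.

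The log-ratio figures in step 3 are not the planned mixed model either. They have no random effects, and the link is inferred because Primary Analysis 1 does not name it.

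A reader might go further and infer that the trial is underpowered, with 4-point power near .55. That figure arises if the pilot's negative binomial dispersion (2.64) also applies to a TAU mean of 9.55. It implies a TAU SD of √(9.55 + 2.64 × 9.55²) = 15.8, whereas the largest printed pilot SD is 10.44. At the other extreme, power is about .93 if 8.4 is the TAU SD and the MI-SI arm is much less variable. The documents support neither extreme.

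The objection does not supply a power for the planned analysis, and that gap remains.

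**Conclusion.** The concern holds in a limited form. The arithmetic is right, but it belongs to a test the trial will not use as its primary analysis, and the SD has no visible source. With the printed follow-up SD, one-sided power for 4 points falls from .81 to .74, and two-sided power from .71 to .62. On a log-ratio scale without a baseline term, simulated power for 4 points is about .66 to .72, and the closed form is a little lower at .61 to .67. The lower end of each range uses a TAU SD of 12.2, somewhat above the printed values. These figures rest on the assumed log link, an MI-SI mean of 5.55 and a TAU mean of 9.55.

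The conclusion that power is adequate for an effect size of .5 is therefore not established for the primary analysis. It is not refuted either. The direction depends on the TAU mean, the dispersion and whether baseline SSI enters the model. The last point is open: the Data Preparation paragraph allows covariates to be added, and baseline adjustment could bring 4-point power above the stated .81.

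**What to change.** In the Power Analysis paragraph:

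1. Label the change-score figures as an approximation to the primary analysis.
2. Give the source of SD 8.4. Otherwise use 9.3 and report .89/.74/.53 one-sided and .81/.62/.40 two-sided.
3. Add power simulated from the model in Primary Analysis 1, including its random effects and stated link, over a stated range of TAU means and dispersions, with and without baseline SSI.
4. Revise the two statements about adequacy (one-sided and two-sided) to match the results.

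The cost is a short simulation and revised wording. N does not change. The stated power will probably become somewhat less favourable.

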## **Human Subjects**

### Risk to Subjects

**Human Participants Involvement and Characteristics.** All participants will be at high risk for emerging suicidality, suicidal behavior, and other negative outcomes. Suicidal behavior is also an outcome and is therefore expected to occur. Safeguards will be built into the study to prevent suicidal behavior before it occurs, and to ensure an appropriate response.

**Potential Risks.** There are no physical risks in this study. Psychological risks are 1) emerging suicidality, 2) distress caused by the personal nature of the interview, recalling distressing events and life problems, and discussing suicide-related issues, and 3) potential need to break confidentiality in the event of suicide risk or violence risk or child abuse.

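### Whether the primary SSI test is one- or two-sided depends on an undefined harm concern that may come from the trial's own data; sidedness should be fixed in advance

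*Combined protocol and SAP*

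**What the plan says.** The Data Preparation paragraph of the Analytical Plan sets the rule for all analyses: intent to treat, "and use one-tailed tests with p < .05 as the cutoff for statistical significance". The primary hypothesis names one direction only, a greater reduction in ideation with MI-SI plus TAU.

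The Power Analysis paragraph adds an exception: if there is a concern that MI-SI caused harm and "the trial is not stopped, we will conduct two-sided analyses instead of the one-sided analyses we proposed". It gives the power for that case with 45 per arm: "we will have .88 power to identify a 5-point difference, .71 power for a 4-point difference, and .47 power for a 3-point difference". It judges this still reasonably adequate.

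The primary model, an over-dispersed Poisson mixed model, "will be used to examine the effect of MI-SI on the severity of SI at 1, 3, and 6 months follow-up". It names no baseline covariate. Data Preparation allows covariates only as a possible response to imbalance found at baseline. Baseline SSI is collected from everyone and is the randomisation stratifier (Randomization paragraph).

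The Data Monitoring Committee section gives that committee a safety-board role, serious adverse events as they occur, and the power to recommend termination. It gives no statistical rule for harm.

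**The concern.** The critical value for the primary outcome is not fixed. It rests on a judgment with no stated definition, decision maker, data source or date, and nothing stops that judgment from using by-arm results. If no concern is raised, a worsening in SSI, however large, cannot be declared significant, although the estimate would still show it. If a concern is raised, a harm tail is opened after data may already have pointed that way.

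The direction matters here. The Risk to Subjects section states: "Psychological risks are 1) emerging suicidality, 2) distress caused by the personal nature of the interview". The Specific Aims say the findings will prepare for a trial on suicidal behavior. A finding of worsening would bear on that decision as much as a finding of benefit, and the Power Analysis itself treats harm as worth two-sided testing.

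**Working it through.** **Inputs (Power Analysis).** Change-score method, one baseline and three follow-up assessments, 45 per arm, and "correlation between baseline and follow-up scores (r = .50), correlation between follow-up scores (r = .70), and standard deviation (sd = 8.4"). Total alpha is .05. The plan does not say how alpha is split after a switch; I assume .025 per tail.

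**1. Reproduce the stated power.** Variance factor for change = (1 + 2 × .70)/3 + 1 − 2 × .50 = .80. Standard error = 8.4 × √(.80 × 2/45) = 1.584. Power = Φ(difference/1.584 − critical value).

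| Points | One-sided (1.645) | Stated | Two-sided (1.960) | Stated |
|---|---|---|---|---|
| 5 | .935 | .94 | .884 | .88 |
| 4 | .811 | .81 | .714 | .71 |
| 3 | .598 | .60 | .474 | .47 |

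All six agree. The power arithmetic is not at issue.

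**2. Benefit-side error.** The switch can only raise the benefit threshold from 1.645 to 1.960, so this error is at most .05.

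**3. Either-direction error.** If no concern is raised, a harm declaration is impossible and the rate is .05. If the concern follows the SSI comparison, a harm tail of up to .025 is added, so the bound is .05 + .025 = .075. The table gives the rate with no true effect if concern is raised when an SSI look at a given fraction of the information shows a z (positive for benefit) below a cut-off. Look times and cut-offs are my assumptions.

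| Information at look | z < 0 | z < −1 | z < −1.645 |
|---|---|---|---|
| .25 | .069 | .064 | .057 |
| .50 | .074 | .070 | .063 |
| .75 | .075 | .074 | .069 |
| Final | .075 | .075 | .075 |

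A stricter cut-off of −1.96 at a quarter of the information gives .055.

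**4. Declaring a true 4-point worsening.** This is 0 if no concern is raised and .71 with a fixed two-sided test. Under the SSI triggers above it runs from .31 (quarter information, z < −1.645) to .71; the −1.96 cut-off at a quarter gives .22. The documents give no basis for choosing within this range.

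**5. Power with baseline SSI as a covariate.** Variance factor = .80 − .50² = .55. Standard error = 8.4 × √(.55 × 2/45) = 1.313.

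| Points | Two-sided, adjusted | One-sided, adjusted |
|---|---|---|
| 5 | .968 | .985 |
| 4 | .861 | .919 |
| 3 | .627 | .739 |

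With a baseline correlation of .30 instead of .50, the adjusted factor is .80 − .09 = .71 and two-sided power at 4 points is .76. The one-sided change score would then have .66.

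**The case against.** The best defence is that one-sided testing for benefit is a legitimate choice, that the switch is written down in advance with its power, and that it only makes a benefit claim harder. That stands for benefit claims. A reader might infer that the benefit p-value has no usable error rate; it has one, at most .05. What is prespecified, however, is that a switch exists, not what sets it off.

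Four further inferences go beyond the documents:

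- **That the error rate is .075.** That is the ceiling. It needs a very late or final look or a weak trigger. The wording about the trial not being stopped suggests a concern raised while it is running, and no by-arm SSI look is planned.
- **That most true worsenings would go undeclared.** This depends on the trigger. Take a concern raised from suicidal-behavior events at yearly looks, with assumed rates of 20% against 10%. Requiring a posterior probability above .95 that MI-SI has the higher rate gives a .31 to .42 chance of declaring a 4-point worsening; requiring .80 gives about .6. Neither rule is in the plan.
- **That one trial in ten would change its verdict.** Estimates from 1.645 × 1.584 = 2.61 to 1.960 × 1.584 = 3.10 points in favour of MI-SI are significant one-sided but not two-sided. Under a true 4-point benefit the estimate falls there with probability .811 − .714 = .10. A concern must also be raised while MI-SI is working; jointly this is at most about .014 under the SSI triggers examined.
- **That harm would go unseen.** The committee can act on it, and for suicidal behavior the plan says "we will use a mixed effects general logistic model to examine the effect size of MI-SI on the incidence of suicidal behavior", so an adverse effect size would be reported.

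It is also fair to say that the covariate would help a one-sided test just as well. At 4 points, two-sided testing costs .919 − .861 = about .06 of power on a like-for-like basis.

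**Conclusion.** The switch is wrong as written: a safety judgment with no stated trigger decides the sidedness of the primary efficacy test. The consequence is moderate. Benefit error is controlled at .05. The either-direction error is about .057 to .075 if the trigger follows the SSI data, on the assumed looks and cut-offs. The chance of declaring a true worsening is undetermined, against .71 at 4 points for a fixed two-sided test. Adding baseline SSI is a free improvement and a separate gain; it is the covariate, not the change of sidedness, that lifts power above the stated figures. All power figures rest on the protocol's linear method and correlations; the planned Poisson mixed model may behave differently.

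**What to change.** In Data Preparation and the Power Analysis, state that the primary SSI test is two-sided at .05 (.025 per tail), fixed before any by-arm data are seen, and delete the switch. Leave harm concerns to the monitoring committee's advice on stopping or continuing. In Primary Analysis 1, enter baseline SSI as a covariate.

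The cost is a few sentences and no new data. With the covariate, two-sided power is .97, .86 and .63 for 5, 4 and 3 points, above the stated .94, .81 and .60; if the baseline correlation is only .30, the 4-point figure is .76. Without the covariate, power is the protocol's own two-sided .88, .71 and .47, which it already accepts. Restoring .81 at 4 points by sample size alone would need 2 × 8.4² × .80 × (1.960 + .881)²/4² = 56.9, so 57 per arm analysed, or 114/.80 = about 143 randomised against the planned 112.
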